10. APPENDICES

Appendix 1 Template for the letter to prescribers including the TROBALT Physician's Guide

Physician address
Date

Dear Physician (or personalise with Dr and surname where possible)

Introducing new Trobalt (retigabine): a first-in-class potassium channel opener for the adjunctive treatment of epilepsy¹

GlaxoSmithKline is pleased to announce the recent marketing authorisation of Trobalt in (country). Trobalt is licensed for partial onset seizures with or without secondary generalisation in adults aged 18 years and above with epilepsy.¹

The approval was supported by the results of the pivotal phase III studies RESTORE 1 and 2, which showed that significantly more patients with uncontrolled epilepsy saw a reduction of 50% or more in seizure frequency compared to placebo when a 600mg/day, 900mg/day or 1200mg/day dose of Trobalt was added to their current anti-epileptic drug (AED) regimen.^{2,3}

Trobalt is a first-in-class AED that is thought to primarily target potassium channels in the brain⁴ which play a major role in seizures and in regulating neuronal function, providing a new therapeutic option for the treatment of uncontrolled epilepsy.^{5,6}

To date, 45 studies investigating Trobalt (phase I, II and III) have been completed evaluating more than 2,000 subjects, including 1,365 patients with epilepsy.⁷

Trobalt has been shown to be generally tolerated with most reported adverse events being transitory, mild to moderate in severity and occurring early during the titration period. Very common side effects were dose-related and included dizziness, somnolence and fatigue¹

AEDs may have specific considerations to ensure appropriate prescribing. With Trobalt, the following advice should be discussed with your patients before initiating therapy.

Trobalt must be taken orally, with or without food, in three divided daily doses. Tablets should be swallowed whole and not chewed, crushed or divided. Trobalt must be titrated to reach an effective dose. The starting dose is 300 mg/day, increased by 150 mg/day weekly according to patient response and tolerability. The maximum total daily dose is 1200 mg/day.¹

Treatment initiation packs are available for patients using the standard dose titration regimen to facilitate the first 2 weeks of therapy, and reach a potentially therapeutic dose of 600 mg/day by the third week of therapy.

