The information in this survey and the Patient Information Leaflet (PIL) should not take the place of talking with your health care professional. If you have any questions about your condition or treatment, or if you would like more information about TROBALT, talk to your health care professional. The Patient Information Leaflet can be obtained from the following website: <http://www.gsk.com/products/prescription-medicines/trobalt.htm>.

Thank You

Appendix 5 Questionnaire for Neurologists who Prescribe AEDs and were Sent the TROBALT Letter Containing the Physician's GuideScreening Questions:

1. Do you agree to take part in this survey?
 - **Yes**
 - No (Exclude)

2. When was the last time you prescribed an anti-epileptic drug for a patient?
 - **Less than a month ago**
 - Between 1 and 2 months ago
 - Between 2 and 3 months ago
 - More than 3 months ago (Exclude)

3. Have you ever prescribed TROBALT?
 - **Yes**
 - No
 - I don't know

4. In which country is your primary medical practice?
 - **Germany**
 - Denmark
 - United Kingdom
 - Switzerland
 - Sweden
 - Spain
 - Slovakia
 - Norway
 - Other (exclude)

[QUOTAS WILL BE ESTABLISHED FOR 200 NEUROLOGISTS FROM UK, SWEDEN, DENMARK, SWITZERLAND, SPAIN, SLOVAKIA, AND NORWAY; AT LEAST 75 SHOULD HAVE PRESCRIBED TORBALT. QUOTA OF 100 NEUROLOGISTS FROM GERMANY, OF WHICH AT LEAST 50 SHOULD HAVE PRESCRIBED TROBALT.]

5. Are you an employee of GlaxoSmithKline or [REDACTED] Corporation?
 - **Yes (Exclude)**
 - **No**

Questionnaire for Neurologists who Prescribe AEDs and Were Sent the TROBALT Letter Containing the Physician's Guide

[CORRECT ANSWERS ARE INDICATED IN BOLD]

6. For which of the following conditions is TROBALT approved for use?
- Migraine
 - **Partial-onset seizures**
 - All types of seizures
 - All of the above
 - None of the above
 - I don't know
7. Is TROBALT indicated for use as monotherapy?
- Yes
 - **No**
 - I don't know
8. What is the maximum recommended daily maintenance dose of TROBALT for most patients? (Please select the best response.)
- 600 mg
 - 900 mg
 - **1200 mg**
 - 2000 mg
 - None of the above
 - I don't know
9. Which one of the following statements is true? (Please select the best response.)
- TROBALT should be taken once a day.
 - TROBALT should be taken twice a day.
 - **TROBALT should be taken three times a day.**
 - TROBALT should be taken four times a day.
 - None of the above
 - I don't know

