10. When increasing the dose, what is the maximum total daily dose at which TROBALT can be increased once every 7 days? (Please select the best response.)
- 50 mg
 - **150 mg**
 - 300 mg
 - 600 mg
 - None of the above
11. Which one of the following statements is true? (Please select the best response.)
- There are no lower age limits for TROBALT usage.
 - The youngest age at which TROBALT can be used is 12.
 - **The youngest age at which TROBALT can be used is 18.**
 - I don't know

Please respond “true,” “false” or “I don’t know” to each of the following questions:

12. The quickest time by which the minimum maintenance dose of 600mg should be reached is the third week?
- **True**
 - False
 - I don’t know
13. For the general population, the recommended total initial dosage should be 150mg per day for one week.
- True
 - **False**
 - I don’t know
14. People taking TROBALT had a higher chance of experiencing which of the following risks in clinical studies? (Please select all that apply)
- **Urinary retention**
 - **Confusional state**
 - **Hallucinations**
 - **Psychotic disorders**
 - Myocardial infarction
 - Renal carcinoma
 - All of the above
 - None of the above
 - I don’t know
15. It is known from controlled studies that adverse events related to voiding dysfunction generally tend to be reported how soon after starting TROBALT?
- Within the first week
 - **Within the first 8 weeks**
 - After 4 months
 - After 12 months
 - I don’t know
16. It is known from controlled studies that confusional state, hallucinations, and/or psychotic disorders generally tend to be reported how soon after starting TROBALT?
- 4 weeks
 - **8 weeks**
 - 12 weeks
 - 16 weeks
 - I don’t know

17. Which of the following urinary symptoms, if any, should you specifically advise patients taking TROBALT to watch out for? (Please select the best response.)
- Pain when urinating
 - Difficulty starting urination
 - Slow stream
 - Inability to pass urine
 - **All of the above**
 - None of the above
 - I don't know
18. According to the TROBALT Physician's Guide, appropriate dose titration may minimize the risk of which of the following adverse events? (Please select the best response.)
- QT prolongation
 - **CNS side effects such as hallucinations**
 - Urinary retention
 - All of the above
 - None of the above
 - I don't know

[DO NOT DISPLAY QUESTIONS 19 and 20 FOR RESPONDENTS FROM SWITZERLAND]

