19. Using the Treatment Initiation Pack, by which week can the patient reach a dose of 600mg/day?
- 2 weeks
 - **3 weeks**
 - 4 weeks
 - 5 weeks
 - None of the above
20. At what dose has TROBALT been shown to produce a possible QT prolonging effect?
- 600 mg
 - 900 mg
 - **1200mg**
 - 1800 mg
 - I don't know
21. For which patients is it recommended that an ECG is recorded before initiating TROBALT? (Please select all that apply.)
- Patients with hypertension
 - **Patients with congestive heart failure**
 - **Patients with ventricular hypertrophy**

- **Patients with hypokalemia**
 - All of the above
 - None of the above
 - I don't know
22. What should you do in a patient with a QTc of **more** than 440ms before starting TROBALT? (Please select the best response)
- Recheck the ECG 1 week after the first dose
 - Recheck the ECG at monthly intervals
 - **Recheck the ECG after reaching the maintenance dose**
 - I don't know
23. Which new cardiac effects in particular should you warn your patients about after prescribing TROBALT? (Please select all that apply)
- Syncope
 - Palpitations
 - Any other symptoms of arrhythmia
 - **All of above**
 - None of the above
24. How would you classify your primary medical specialty?
- Neurology
 - Neurosurgery
 - Epileptology
 - Other (specify) _____ [FREE TEXT]
 -
25. Have you read the TROBALT information letter that was sent at the launch of TROBALT?
- Yes
 - No
 - I don't know
26. From which of the following sources have you learned about the risks associated with use of TROBALT? (Please select all that apply)
- TROBALT launch letter
 - GlaxoSmithKline medical information
 - Other health care professionals
 - GlaxoSmithKline promotional materials
 - GlaxoSmithKline sales representatives
 - Journal article
 - GlaxoSmithKline-sponsored educational meeting
 - None of the above

27. What is your gender?

- Male
- Female

28. For how many years have you been in medical practice?

- Less than 3 years
- 3-5 years
- 6-10 years
- 11-15 years
- 16-20 years
- More than 20 years
- Prefer not to answer

29. Do you agree to provide your name and address so that we can issue a payment for your time in completing this survey?

- Yes (Record name and address)
- No

Name _____

Address _____

[CLOSING] That ends the survey. Thank you again for your help. The correct answers to the questions about TROBALT follow.

The following are the correct answers to the survey questions about TROBALT.

For which condition is TROBALT approved for use?

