- **Partial-onset seizures**

Is TROBALT indicated for use as monotherapy?

- **No**

What is the maximum recommended daily maintenance dose of TROBALT for most patients?

- **1200 mg**

Which one of the following statements is true? (Please select the best response.)

- TROBALT should be taken once a day.
- TROBALT should be taken twice a day.
- **TROBALT should be taken three times a day. [CORRECT RESPONSE]**
- TROBALT should be taken four times a day.

When increasing the dose, what is the maximum total daily dose at which TROBALT can be increased once every 7 days?

- **150 mg**

Which one of the following statements is true?

- There are no lower age limits for TROBALT usage.
- The youngest age at which TROBALT can be used is 12.
- **The youngest age at which TROBALT can be used is 18. [CORRECT RESPONSE]**

The quickest time by which the minimum maintenance dose of 600mg should be reached is the third week?

- **True**

For the general population, the recommended total initial dosage should be 150mg per day for one week.

- **False**
The starting dose is 300 mg/day

People taking TROBALT had a higher chance of experiencing which of the following risks in clinical studies?

- Urinary retention
- Confusional state
- Hallucinations
- Psychotic disorders

It is known from controlled studies that adverse events related to voiding dysfunction generally tend to be reported how soon after starting TROBALT?

- **Within the first 8 weeks**

It is known from controlled studies that confusional state, hallucinations, and/or psychotic disorders generally tend to be reported how soon after starting TROBALT?

- **8 weeks**

Which of the following urinary symptoms, if any, should you specifically advise patients taking TROBALT to watch out for?

- Pain when urinating
- Difficulty starting urination
- Slow stream
- Inability to pass urine
- **All of the above**

According to the TROBALT Physician's Guide, appropriate dose titration may minimize the risk of which of the following adverse events?

- **CNS side effects such as hallucinations**

[DO NOT DISPLAY THE FOLLOWING TWO QUESTIONS FOR RESPONDENTS FROM SWITZERLAND]

Using the Treatment Initiation Pack, by which week can the patient reach a dose of 600mg/day?

- **3 weeks**

At what dose has TROBALT been shown to produce a possible QT prolonging effect?

- **1200mg**

For which patient is it recommended that an ECG is recorded before initiating TROBALT?

- Patients with congestive heart failure

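### Neurologist items Q10 and Q19 have stems that do not match their (correct) keys, and Q10, Q19 and Q23 offer no 'I don't know' although every question must be answered

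*Protocol*

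**What the plan says.** The letter to prescribers (Protocol, Appendix 1) is the material whose uptake the neurologist survey tests. It gives the schedule as "The starting dose is 300 mg/day, increased by 150 mg/day weekly according to patient response and tolerability" and the ceiling as "The maximum total daily dose is 1200 mg/day". It describes the treatment initiation packs as a means "to facilitate the first 2 weeks of therapy, and reach a potentially therapeutic dose of 600 mg/day by the third week of therapy".

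Three items in Appendix 5 draw on this passage of the letter:

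- **Q8** asks "What is the maximum recommended daily maintenance dose of TROBALT for most patients". The options are 600, 900, 1200 (keyed) and 2000 mg, 'None of the above' and 'I don't know'.
- **Q10** asks "When increasing the dose, what is the maximum total daily dose at which TROBALT can be increased once every 7 days", followed by an instruction to pick the best response. The options are 50, 150 (keyed), 300 and 600 mg and 'None of the above'.
- **Q19** asks "Using the Treatment Initiation Pack, by which week can the patient reach a dose of 600mg/day". The options are 2, 3 (keyed), 4 and 5 weeks and 'None of the above'. It carries no best-response instruction and is not shown to Swiss respondents.

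Section 3.3.2 fixes the question order, prevents going back and requires an answer to every question. Section 4.4 tabulates the proportion correct separately for each item of the physician instrument. Section 6.2.2 adds a confidence interval for each risk question and the distribution of responses to multiple-choice questions.

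**The concern.** In both items the stem asks for one kind of quantity while the key is another.

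Q10 asks for a total daily dose, in almost the words the letter uses for its ceiling, but the key is a weekly increment. Q19 asks for a week in sequence, but its options read as lengths of time.

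A neurologist who knows the schedule could therefore be recorded as not knowing it. One who does not know it has no way to say so, and must guess or fall back on 'None of the above'.

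The plan combines nothing into a score, so each item's proportion correct is read as a finding about that message. Titration is relevant to risk: the letter links proper titration to fewer central nervous system events. A figure that mixes knowledge with misreading is a poor guide to whether the titration message needs revising.

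**Working it through.** **1. Rebuild the titration.** The inputs are the 300 mg/day start and the 150 mg/day weekly step, both from the Appendix 1 letter.

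Dose in week w = 300 + 150 × (w − 1) mg/day.

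| Week | Days | Dose (mg/day) | Weeks completed before it |
|---|---|---|---|
| 1 | 1–7 | 300 | 0 |
| 2 | 8–14 | 450 | 1 |
| 3 | 15–21 | 600 | 2 |

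Solving 300 + 150 × (w − 1) = 600 gives w = 3. This reproduces the letter's third week and Q19's key. The first day at 600 mg/day is 7 × 2 + 1 = day 15.

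**2. Compare with Q19.** As a week in sequence, the answer is the third. As elapsed time, it is two weeks. The options are worded as elapsed time and the stem as a week in sequence. Q12, which asks nearly the same thing as a true/false statement, names the third week outright and does not have this problem.

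**3. Compare with Q10.** In the letter, the total daily dose runs from 300 mg/day at the start to 1200 mg/day at most. The key of 150 mg is below 300 mg, so it cannot be a total daily dose on this schedule. The letter's maximum, 1200 mg, is not among the options, which leaves 'None of the above' for anyone who takes the stem at its word. As a weekly increment, 150 mg is right and unique.

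**4. Count the 'I don't know' options.** Q6 to Q23 gives 23 − 6 + 1 = 18 items. The option is absent from Q10, Q19 and Q23 and present in 18 − 3 = 15.

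**5. Direction of any bias.** The protocol gives neither the share who know an item nor the share who misread it, so the following is illustration only.

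- Suppose 60% know the fact. If everyone else guesses evenly among five options, the recorded figure is 60 + 40/5 = 68%.
- If no one guesses correctly but 10% of those who know misread the item, it is 60 × 0.90 = 54%.
- With both at once, it is 54 + 8 = 62%.

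The two faults pull in opposite directions, so not even the sign of the net error can be fixed from the documents.

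**6. What the response table can show.** The distribution under Section 6.2.2 will show how many chose '2 weeks' or 'None of the above'. It cannot show why. In Q10, 'None of the above' is open both to the literal reader and to the respondent who does not know.

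**The case against.** The case for leaving the items alone has real weight.

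- **Q10 gives several pointers to the intended answer.** It opens by referring to a dose increase, speaks of a seven-day interval and asks for the best response. Q8 has already asked for the maximum dose. The words 'total daily' also do useful work: with three divided doses, 150 mg/day is 150/3 = 50 mg per dose, and 50 mg is one of the options. Most respondents will probably reach 150 mg. This stands, and it limits the claim to some respondents who might go astray. A reader might infer that anyone taking the stem literally must choose 'None of the above'; the best-response instruction and the rest of the stem do not support that.
- **Q19's stem points to its key.** It asks for a week, in line with the letter and with Q12. Two weeks is also the period the initiation pack covers, so a '2 weeks' answer may be a genuine error about the schedule. This stands too, and it is why the response table cannot settle the matter.
- **The closing list might seem to teach a wrong maximum dose.** It repeats the Q10 stem with 150 mg. But it gives 1200 mg as the maximum two entries earlier and says "The starting dose is 300 mg/day" three entries later, then refers readers to the Physician's Guide and the prescribing information. The harm is negligible.
- **'I don't know' is not promised on every item.** That is so. But 15 of 18 items have it and answers are compulsory, so the three exceptions are measured differently from the rest without a stated reason.
- **The items are about dosing, and the survey is translated.** The outcome is framed around risks, although Section 4.4 tabulates every item. Translation may remove or keep the ambiguity, so Q19's use in seven of the eight countries (8 − 1) does not show that seven countries are affected.

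**Conclusion.** The point holds as a wording defect in two of the 18 knowledge items, together with a missing response option in three. It belongs to the instrument, so an analysis plan would not be expected to resolve it.

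A reader might infer that the answer keys are wrong. They are not: 150 mg as the weekly step and the third week for 600 mg/day both follow from the letter. Nor does anything here touch the other knowledge items, the sample size or the design.

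The size and direction of the error are unknown. It is probably small, because both items contain pointers to the intended reading and Q12 gives a separate measure of nearly the same fact as Q19. The conclusion rests on the English text in Appendix 5 and assumes that the translations follow it. The change is worth making because these proportions are reported singly as primary outcomes, later analysis cannot separate misreading from ignorance, and the correction is nearly free.

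**What to change.** Before translation and programming:

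1. **Q10:** ask for the largest amount by which the total daily dose may be raised at each weekly step. Keep the options and the 150 mg key.
2. **Q19:** relabel the options 'Week 2', 'Week 3', 'Week 4' and 'Week 5', keyed to 'Week 3'.
3. **Q10, Q19 and Q23:** add 'I don't know'.
4. **Closing answer list:** use the new Q10 stem, and give 'Week 3' for Q19.

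The cost is a text edit to three items and two closing entries. Sample size, timing and the Swiss skip instruction are unaffected, and no item needs to be moved or dropped.

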- 1) 250 patients recruited from across the following countries (United Kingdom, Sweden, Denmark, Switzerland, Spain, Slovakia and Norway) and up to 100 patients from Germany who are currently using or have filled a prescription for TROBALT at least once in the last 3 months.
- 2) 200 neurologists who have prescribed an anti-epileptic drug (AED) at least once in the last 3 months, and who were on the list to which a letter containing the Physician's Guide for TROBALT was distributed from across the following countries (United Kingdom, Sweden, Denmark, Switzerland, Spain, Slovakia and Norway). At least 75 of the neurologists will have prescribed TROBALT. The survey will also aim to include up to 100 neurologists from Germany of which approximately 50 will have prescribed TROBALT.

Patients eligible for the survey will be asked to take the survey online or via a telephone interview if the latter is preferred. Neurologists will be invited to take the survey online.

The selected countries were the first five countries to launch TROBALT (Germany, Denmark, United Kingdom, Switzerland and Sweden) and an additional three countries with launch in 2011, but with relatively high rates of uptake of TROBALT (Spain, Slovakia and Norway). The selection of countries includes Switzerland, which is not part of the European Union. However, the key messages regarding the risks with TROBALT are in alignment. The rationale for surveying the first five countries to launch is so that any issues identified from these countries regarding the effectiveness of the Physician's Guide and PIL in communicating the risks of TROBALT can be addressed as soon as possible, and the key messages can be revised in a timely manner. In addition, these countries are likely to provide the greatest number of neurologists with experience of prescribing TROBALT, and their patients.

Study Endpoints/Assessments

The primary outcome of the survey is the proportion of patients/neurologists providing correct responses to a series of questions concerning the significant risks associated with TROBALT. The risks evaluated will be those described in the TROBALT PIL and in the Physician's Guide.

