3.3.1. Questionnaire Structure

Each survey will be composed of multiple choice and close-ended questions. There will be no open-ended questions included. For statements or questions that use "true" or "yes" vs. "false" or "no" response options, the desired response for key risk messages is generally "true" or "yes" indicating knowledge of, or behavior in accordance with, the objectives of the program. However, some questions are formatted to have the respondent disagree with the statement as written by providing response options of "false" or "no" to avoid having the same affirmative answer for all desired responses.

Both physicians and patients will be provided a unique code in the survey invitation letter and will be asked to provide the unique code to gain access to the online survey or when calling the Survey Coordinating Center. The code will be deactivated after use to minimize the possibility for fraud.

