3.3.2. Measures to minimise bias in the surveys

The following are measures to minimise bias in the surveys:

- Telephone interviewers are highly trained and use a standardized script to administer interviews.
- All questions will be programmed to ensure that questions are asked in the appropriate sequence. Skip patterns will be clearly indicated. Respondents cannot go back to a question once the question has been answered and cannot skip ahead. All questions must be answered in order to complete the survey.
- Response options presented in a list will be randomized to minimize positional bias.
- Programming will be reviewed by quality control and simulated users (User Acceptance Testing) prior to implementing the survey.

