6.2.2. Neurologist survey analysis

The primary outcome is the proportion of neurologists answering each question of the understanding of the risks associated with TROBALT correctly. Point estimates for the proportion with correct responses, and associated confidence intervals, will be calculated for each question about the risks of TROBALT. In the case of multiple choice questions, the number and proportion of neurologists reporting each response will also be provided.

The proportion of correct answers to survey questions will be summarised overall, and separately for those neurologists who have prescribed TROBALT. Exploratory analyses may include stratification by country.

The survey results will be presented with Germany included in the overall study population, then separately for Germany and the remaining specified European countries.

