Appropriate dose titration may minimise the risk of central nervous system-related adverse events, including hallucination and psychotic disorders.

Date of preparation: May 2011
NECE/RTG/0033/11

Prescribing Information is available on the back page

Trobalt™
retigabine tablets

1. Urinary effects

Urinary retention, dysuria and urinary hesitation were reported in controlled clinical studies with Trobalt, generally within the first 8 weeks of treatment. Trobalt must be used with caution in patients at risk of urinary retention, and it is recommended that patients are advised about the risk of these possible effects.¹

Does your patient have symptoms of urinary retention e.g. hesitancy, poor stream?

Does your patient take drugs that can cause urinary retention e.g. anticholinergics?

Is your patient able to communicate new symptoms of urinary retention?

2. QT interval prolongation

A study of cardiac conduction in healthy subjects has demonstrated that Trobalt titrated to 1200 mg/day produced a QT prolonging effect. A mean increase in Individual Corrected QT Interval (QTcI) of up to 6.7 ms (upper bound of 95% one-sided CI 12.6 ms) was observed within 3 hours of dosing.¹

Caution should be taken when Trobalt is prescribed with medicinal products known to increase QT interval and in patients with known prolonged QT interval, congestive cardiac failure, ventricular hypertrophy, hypokalaemia or hypomagnesaemia and in patients initiating treatment who are 65 years of age and above.¹

In these patients it is recommended that an electrocardiogram (ECG) is recorded before initiation of treatment with Trobalt and in those with a corrected QT interval >440 ms at baseline, an ECG should be recorded on reaching the maintenance dose.¹

Does your patient have a history of cardiac disease?

Does your patient take drugs that are known to cause QT prolongation?

Retigabine has not been shown to cause cardiac arrhythmias in the randomised clinical trials, however patients should be advised to report new symptoms that might indicate a prolonged QT interval, for example palpitations, syncope.

3. Psychiatric effects

During controlled clinical studies, confusional state, psychotic disorders and hallucinations were reported, generally within the first 8 weeks of treatment. It is recommended that patients are

Date of preparation: May 2011
NECE/RTG/0033/11

Trobalt™
retigabine tablets

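### Neurologist Question 22 presupposes a repeat ECG, so it tests only the timing and cannot record the belief that none is needed

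*Protocol*

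**What the plan says.** The Physician's Guide letter (Protocol, Appendix 1, QT interval prolongation) states that in patients with a baseline corrected QT above 440 ms "an ECG should be recorded on reaching the maintenance dose". That sentence tells the neurologist both that another ECG is due and when.

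Appendix 5, Question 22 tests this message with four options: "Recheck the ECG 1 week after the first dose"; "Recheck the ECG at monthly intervals"; a recheck after reaching the maintenance dose, which is the keyed answer; and *I don't know*.

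Three other provisions bear on the item:

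- Section 3.3.2: "All questions must be answered in order to complete the survey".
- Section 3.3.1: "There will be no open-ended questions included". A few background items do have a free-text line, but Question 22 has none.
- Section 6.2.2: besides the proportion correct, for multiple choice questions "the number and proportion of neurologists reporting each response will also be provided".

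The Protocol Summary and Section 3.2.1 give the reason for surveying the first launch countries: communication problems can be found and "the key messages can be revised in a timely manner".

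**The concern.** All three substantive options share the same action and differ only in time. The item therefore tells the respondent that a repeat ECG is expected and asks only about timing. A neurologist who believes that the baseline ECG is enough has no matching answer and cannot skip the question, so that belief is recorded either as *I don't know* or under a guessed time.

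The belief matters for safety, because it leaves a patient with a QTc above 440 ms without the on-treatment ECG that the letter asks for. It also matters for the survey's purpose. Not knowing that a repeat is due and knowing it but mistaking the time are different failures of the letter, and they would plausibly lead to different rewording. A table of the options offered cannot tell them apart. In addition, each item's proportion correct is a primary outcome (Section 4.4), and one of the guessed times scores as correct.

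**Working it through.** **1. Message against item.**

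| Part of the letter's message | Tested by Question 22? |
|---|---|
| A further ECG is needed if baseline QTc is above 440 ms | No: 3 of 3 substantive options assume it |
| It is done on reaching the maintenance dose | Yes: 1 of 3 times is keyed |

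**2. Where a neurologist who believes that no repeat is needed can land.** *I don't know*: not correct, rightly. One week: not correct, rightly. Monthly: not correct, rightly. Maintenance dose: correct, wrongly. Only the last route biases the proportion correct. All four hide the belief.

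**3. Does another item cover the gap?** There are 18 knowledge items, Questions 6 to 23.

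- Ten offer *None of the above*: 6, 8, 9, 10, 14, 17, 18, 19, 21 and 23.
- Question 11 has its own null answer (no lower age limit).
- Questions 7, 12 and 13 are yes/no or true/false.
- That leaves 15, 16, 20 and 22, which take their premise as given.

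Questions 15 and 16 ask when urinary and psychiatric events occur, but Question 14 ("People taking TROBALT had a higher chance of experiencing which of the following risks in clinical studies") has already tested whether those risks exist. Question 20 asks for a study finding. Question 22 is the only one of the four that asks what the physician should do, and no other item tests whether the ECG is repeated. Its neighbours 21 and 23, on the same cardiac topic, both offer *None of the above*.

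**4. The plan's precision figure.** The 95% margin is 1.96 × √(p(1−p)/n).

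- n = 250, p = 0.60: 1.96 × √(0.24/250) = 6.07 points. Section 7 states 6.0, so it is reproduced to rounding.
- n = 300 (200 plus up to 100 from Germany), p = 0.60: 1.96 × √(0.24/300) = 5.54 points. Table 1 gives 5.7.

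The 60% is the protocol's illustration for patients and serves here only as a yardstick. The full 300 applies, because the Swiss skip covers Questions 19 and 20 only.

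**5. Possible overstatement of the proportion correct.** In points it is 100 × n0 × f × k, where n0 is the share holding the belief, f the fraction of them who guess a time instead of choosing *I don't know*, and k the chance that a guess hits the key. None of the three is in the documents. Assumed ranges: n0 = 10% or 20%; f = 0 to 1; k = 0.2 to 0.5, with even guessing over three times giving 1/3.

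| n0 | f | k = 0.2 | k = 1/3 | k = 0.5 |
|---|---|---|---|---|
| any | 0 | 0 | 0 | 0 |
| 10% | 0.5 | 1.0 | 1.7 | 2.5 |
| 10% | 1 | 2.0 | 3.3 | 5.0 |
| 20% | 0.5 | 2.0 | 3.3 | 5.0 |
| 20% | 1 | 4.0 | 6.7 | 10.0 |

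**6. When does it exceed the sampling margin?** Solve f = 0.0554/(n0 × k).

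- n0 = 20%, k = 0.5: 0.0554/0.100 = 0.55.
- n0 = 20%, k = 1/3: 0.0554/0.0667 = 0.83.
- n0 = 20%, k = 0.2: 0.0554/0.040 = 1.39, above 1, so never.
- n0 = 10%, k = 0.5: 0.0554/0.050 = 1.11, so never in the assumed range.

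With Table 1's 5.7 in place of 5.54, the first two become 0.57 and 0.86.

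**The case against.** The case against is substantial. Nothing in Question 22 is misstated or miskeyed. An item may legitimately test the timing of a recommended action, and whoever knows the timing also knows that a repeat is due. Anyone else can choose *I don't know*, which is scored not correct. Section 6.2.2 promises counts of the responses offered, not a diagnosis of wrong answers. A poor score would send the sponsor back to the same sentence of the letter in any case, and the documents set no rule linking types of error to types of revision. Question 20 also presupposes its premise, the QT effect itself, and Question 14 does not list QT prolongation.

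Most of this stands. The effect on the primary outcome may be zero, and the claim that the two errors call for different revisions is a judgement. What remains is that *I don't know* mixes uncertainty with a confident wrong belief, and that Question 22, unlike Question 20, concerns what is done for a patient. Nor can this be left to an analysis plan, because no analysis recovers an answer that was never offered.

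Two stronger inferences are tempting and unsupported. A reader might infer that the Question 22 result will be materially inflated; the documents give none of the three quantities needed to show that. A reader might also treat everyone scored not correct as a measure of how many could hold the belief. The same count would apply to any item missing any distractor, so it says nothing specific about Question 22.

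**Conclusion.** The concern holds as a limited defect of item design. Question 22 cues the need for a repeat ECG, tests only its timing, and cannot record the belief that no repeat is needed, although the letter's message covers both. This follows from the text and needs no assumption. The main consequence is that the planned per-response table cannot separate neurologists unaware that a repeat is needed from those who have the wrong time.

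Any overstatement of the proportion correct is secondary and of unknown size. Within the assumed ranges it lies between 0 and about 10 points, the top needing a 20% belief share, everyone guessing, and half of the guesses hitting the key. It scales in proportion to each assumed input. It is larger than the 5.5-point margin only at the 20% share, and then only if more than about 55% guess (k = 0.5) or about 83% guess (k = 1/3).

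This is one of 18 descriptive items, and the protocol sets no pass threshold. The change is worth considering because it is cheap and matches the questionnaire's own practice; the survey does not depend on it.

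**What to change.** Add two incorrect options to Question 22: *No further ECG is needed* and, in line with Questions 21 and 23, *None of the above*, which catches other beliefs such as not starting the drug. Leave the key unchanged. Report both counts in the per-response table already planned in Section 6.2.2, and describe the *No further ECG is needed* share as an approximate indicator, since unsure respondents may also choose it.

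The cost is two response lines to program and translate. Sample size and analysis method are unaffected. The proportion correct may come out slightly lower.
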